The purpose of the Endurant Evo International Clinical Trial is to evaluate the safety and effectiveness of the Endurant Evo AAA Stent graft system for endovascular treatment of subjects with infrarenal abdominal aortic or aortoiliac aneurysms. The clinical evidence collected as part of this trial is expected to be used to support regulatory approval and subsequent commercialization of the Endurant Evo AAA Stent graft system in multiple international geographies.

Data collected during this trial may also be used in conjunction with data collected during a concurrently enrolling IDE trial to support PMA Approval of the Endurant Evo AAA Stent graft system in the United States.

The primary safety objective is to evaluate the safety of the Endurant Evo AAA stent graft system for the endovascular treatment of infrarenal abdominal aortic or aortoiliac aneurysms. Safety will be assessed through the proportion of subjects who have a Major Adverse Events (MAE) reported within 30 days post-implantation.

The primary effectiveness objective is to evaluate successful delivery and deployment of the Endurant Evo AAA stent graft system with successful removal of the delivery system during the index procedure.

Secondary objectives include descriptive analyses of secondary endpoints as well as acute procedural and clinical utility measures.

3. Study Design

The Endurant Evo International Clinical Trial is a prospective, multi-center, pre-market, non-randomized, single-arm trial.

3.1. Treatment and Subject Enrollment

The study population will include those subjects who are appropriate candidates for endovascular repair of infrarenal abdominal aortic or aortoiliac aneurysms, and who meet the Inclusion/Exclusion criteria (defined in the Clinical Investigation Plan Section D).

For subjects that are treated with the bifurcated stent graft minimal 3 pieces will be implanted in the target segment; one bifurcated stent graft component and 2 limb stent graft components. For subjects that are treated with the AUI component approximately 2 pieces will be implanted in the

target segment; the AUI stent graft component and one limb stent component. Additional stent graft extensions might be needed to cover the complete target lesion length.

A sample of 40 subjects will be treated and evaluated at the 30-day primary safety endpoint. Data from these 40 subjects will be analyzed and used to support regulatory approval. All subjects treated will continue to be followed under this investigational protocol beyond the 30-day primary endpoint until 5 years post-implantation.

Subjects will have required follow-up evaluations at the following time points:

- 1 month following the index procedure
- 6 months following the index procedure
- 12 months following the index procedure
- Annually thereafter, until 5 years post index procedure

In addition to the 40 subjects to support regulatory approval, approximately 30 additional subjects may be treated to support geography-specific regulatory requirements. For these subjects, all inclusion/exclusion criteria, study methods, follow-up schedule and data-collected will be identical to the first 40 subjects.

Approximately 10 sites will participate in the clinical study. For the initial 40 subjects to be analyzed, no more than 20% (i.e. 8 subjects) will be treated from a single investigational site. Enrollment will be halted at sites that reach the 20% enrollment cap. Following enrollment of the first 40 subjects, up to approximately 30 additional subjects can be enrolled and a site where enrollment has been halted may resume enrolling. For the total cohort of 70 subjects again no more than 20% of subjects will be treated from a single investigational site which results in a maximum enrollment per site of 14 subjects.

The total enrollment period is not expected to exceed 12 months. All treated subjects will be followed until 5 years post-implantation. Thus total study duration from first subject treated to final subject exit could approach 6 years.

3.2. Sample Size Consideration

A sample of 40 subjects will be treated and analyzed to support regulatory approval. The sample size of 40 subjects is considered adequate to assess the primary safety endpoint, which is defined as the proportion of subjects experiencing a MAE within 30 days post-implantation.

Considering the reported MAE rate from the ENGAGE Post-Approval Study (PAS), which evaluated the long-term safety and effectiveness of the Endurant Stent graft system in 328 subjects¹, it is estimated that 2 of 40 (5%) subjects treated with Endurant Evo AAA stent graft system will experience a MAE. The precision of this assumed 5% point estimate can be assessed by calculating the difference from the 1-sided 95% upper confidence limit. This difference, or margin of error, is calculated to be < 10% for the Endurant Evo International Clinical Trial and is therefore considered adequate to assess the primary safety endpoint^{2,3}.

3.3. Analysis Strategy

The Endurant Evo International Clinical Trial is not hypothesis driven; all endpoints will be analyzed descriptively.

4. Analysis Sets

4.1. Primary analysis set

All analysis will be performed on the intent-to-treat (ITT) analysis set, which includes all subjects who underwent the arterial access with an attempt to introduce the Endurant Evo AAA stent graft.

4.2. Subset

Subset analysis will be performed by-sex for the primary endpoints descriptively and reviewed for clinical significant difference.

5. Endpoints

Primary Safety Endpoint

The primary safety endpoint is defined as the proportion of subjects experiencing a MAE within 30 days post-implantation. MAEs include the occurrence of any of the following events:

- All-cause mortality
- Bowel ischemia
- Myocardial infarction
- Paraplegia
- Procedural blood loss ≥ 1000 cc
- Renal failure
- Respiratory failure
- Stroke

Primary Effectiveness Endpoint

Technical success at the index procedure (as assessed intra-operatively) is defined as successful delivery and deployment of the Endurant Evo AAA Stent graft system in the planned location and with no unintentional coverage of both internal iliac arteries or any visceral aortic branches and with successful removal of the delivery system.

Secondary Endpoints

- All cause-mortality within 30, 183, and 365 days
- Aneurysm-related mortality within 30, 183, and 365 days
- Secondary procedures to correct Type I and III endoleaks within 30, 183 and 365 days
- Secondary endovascular procedures within 30, 183 and 365 days
- Serious adverse events within 30, 183 and 365 days
- Aneurysm rupture within 30, 183 and 365 days
- Conversion to open surgery within 30, 183 and 365 days
- Major adverse events within 183 and 365 days
- Stent graft migration at 12-month follow-up visit (as compared to 1-month imaging)
- Aneurysm expansion > 5 mm at 12-month follow-up visit (as compared to 1-month imaging)
- All endoleaks based on imaging findings at 1- month, 6-month and 12-month visits
- Stent graft occlusion based on imaging findings through 6 months and 12 months
- Device deficiencies based on imaging findings through 6 months and 12- months

Secondary endpoints will be assessed at annual follow-up visits until 5 years post-implantation.

Additional Observations

The following acute procedural observations and clinical utility measures will be reported:

- Mean duration (min) of procedure (time between initial skin access to final skin closure)
- Proportion of subjects who underwent general/local/epidural/spinal anesthesia
- Proportion of subjects who underwent unilateral/bilateral percutaneous access
- Proportion of subjects requiring blood transfusions, excluding cell saver
- Mean volume (cc) of estimated blood loss
- Mean duration (min) of radiation exposure
- Radiation exposure (mGy)
- Mean length of time (hours) in intensive care unit
- Mean length of time (days) of hospital stay (from the index procedure to hospital discharge)

Health-related quality of life outcomes will be assessed at baseline, 1-month, 6-month and 12-month follow-up visits using the EQ5D questionnaire.

6. Definitions

Detailed definitions for secondary endpoints are provided in Clinical Investigational Plan Appendix L.2.

7. Interim Analysis

No interim analysis is planned prior to the regulatory submission.

8. Statistical Methods of Analyses

8.1. General consideration

All endpoints will be analyzed descriptively. In general, qualitative parameters will be described by their distribution frequencies; quantitative parameters will be described by their mean, standard deviation, minimum, maximum, median, and number of subjects with assessable data.

The survival from all-cause mortality over one year time or longer will be described by the Kaplan-Meier survival curve and the associated Kaplan-Meier estimate will be calculated along with its standard error using the Greenwood method.

For events such as AEs, deaths and secondary procedures, that can occur or are observed at any time during the study, no time window will be applied. For such events, an event that occurs “within 1 month or 30 days” is an event that takes place between Days 0 to 30, inclusive.

Similarly, an event that occurs “within 12 months or 365 days” is an event occurring between Day 0 to Day 365, inclusive. Date of event onset will be used to determine when the event occurred. Day 0 is referring to the day of index procedure.

For image-based assessments, such as stent-graft endoleak, patency, and other observations, the following time windows will be applied for by-visit data summaries:

Table 1: Time Windows for Statistical Analyses

Study Visit	Target Day	Time Window
Implant	Day 0	Day 0
1 Month	Day 30	1 – 90 days
6 Months	Day 183	91 – 304 days
12 Months	Day 365	305 – 548 days
2 Year	Day 731	549 – 913 days
3 Year	Day 1096	914 – 1278 days
4 Year	Day 1461	1279 – 1644 days
5 Year	Day 1826	1645 – 2009 days

If different type of images are used but have different finding in the same time window, the imaging technique and sensitivity matrix (Appendix 12.1) will be applied. Finding from higher visibility image will be used for analysis. If there are two or more assessments from the same type of image in the same time window, then the assessment closest to the target day will be used in the analysis of event rate at a given time point.

Statistical analyses for this study will be performed using the Statistical Analysis System (SAS) for Windows (Version 9.1 or higher) or other widely-accepted statistical or graphical software.

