Abdominal X-rays should be completed via a four-view kidney, ureter, bladder (KUB) X-ray. Posterior/anterior (PA) and lateral images are recommended for visualization of the stent graft. Ensure the entire device is captured on images for assessment.

If conversion to open repair is required during the follow-up period, then the subject will be followed for 30 days after the conversion, at which time the subject will be exited from the study. Please refer to Device Explant and Returned Procedures/Products section, located in E.6.3 of the protocol.

F.3 Data Collection Requirements

Clinical data will be collected preoperatively to establish eligibility, at baseline, during the index procedure, throughout the hospital stay, and postoperatively at the required (and any interim imaging) follow-up visits described in Section F.2. The data collection schedule is summarized in Table F-2. Imaging source data will be sent to the Core Lab for analysis up to the 60-month follow-up visit. Any interim imaging of the stent graft region but not linked to a study visit should be sent to the Core Lab (e.g. imaging performed as standard of care beyond the protocol required time points and/or when performed further to any issue observed at previous imaging Follow-up). This also includes Interim imaging performed, as recommended per the most recent DMC Surveillance and Management letter. All images taken from the stent graft region must be assessed by the site. Any findings that meet the requirements in the flowchart (Appendix L.5) must be reported on the applicable eCRF. Study data will be collected using electronic case report forms (eCRFs) as described in Section G.1. Clinical investigators must electronically review and approve all eCRFs. The monitoring strategy will be defined in the monitoring plan.

Table F-2: Data Collection Schedule

DATA	Screening/ Baseline	Index Procedure	Hospital Discharge	1-Mo. FU (±15 days)	6-Mo. FU (±30 days)	12-Mo. FU (-30/+56 days)	2 Yr. FU (±56 days)	3-5 Yr. FU (±56 days)
Informed consent	✓							
Inclusion / Exclusion criteria	✓							
Physical examination	✓			✓	✓	✓	✓	
Medical history	✓							
Current health status and risk factors	✓							
Laboratory tests at screening:Creatinine, INR ^d	✓							
Device and procedure information		✓						
Implant adjunctive procedures		✓						
Hospital discharge information			✓					
Medications	✓			✓	✓	✓	✓	
Adverse event assessment		✓	✓	✓	✓	✓	✓	✓
EQ5D questionnaire	✓			✓	✓	✓		
IMAGING								

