$n = \text{No. of Subjects Who Had Readable Images}$	No. of subjects who had a readable image within the 1-month window.	No. of subjects who had a readable image within the 6-month window.	No. of subjects who had a readable image within the 12-month window.
Event rate = m/n	Through 1 Month	Through 6 Months	Through 12 Months
$m = \text{No. of Subjects Who Had Event(s)}$	No. of subjects who had an event with scan day within the 1-month window.	No. of subjects who had an event with scan day within 1- or 6-month windows.	No. of subjects who had an event with scan day within 1-, 6- or 12-month windows.
$n = \text{No. of Subjects Who Had Readable Images}$	No. of subjects who had a readable image within the 1-month window.	No. of subjects who had an event (counted in m) or had a readable image	No. of subjects who had an event (counted in m) or had a readable image

		within the 6-month window.	within the 12-month window.
--	--	----------------------------	-----------------------------

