12.1. Imaging Technique and Sensitivity

Anatomy/Stent Graft Issue Detected	CT with contrast	CT without contrast	MRA	MRI	Abdominal X-ray	Duplex CDUS (Ultrasound)	Angiogram, Aortogram and Arteriogram
AAA Diameter and Length	1	2	1	2	4	3	3
Stent graft migration	1	2	1	2	3	4	2-3
Stent graft fracture	2	3	2	3	1	4	2-3
Stent graft kinking	2	3	2	3	1	4	2-3
Stent graft twisting	2	3	2	3	1	4	2-3
Stent graft patency	1	4	1	4	4	2	2-3
Endoleaks	1	4	1	4	4	2	2-3
Occlusion	1	4	1	4	4	2	2-3
Stenosis	1	4	1	4	4	2-3	2-3
Stent Graft Fabric Defect	1	4	1	4	4	4	2-3
1= Highly visible		2 = visible		3 = Not very visible (potential artifacts)			4 = Invisible

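### SAP 8.1 chooses between image types by visibility rank and ignores dates, so an earlier clear X-ray can override a stent fracture first seen on a later CT in the same window

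*SAP*

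**What the plan says.** SAP 8.1 assigns images to the analysis windows of Table 1 and gives two selection rules.

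- **Different image types.** The trigger is "If different type of images are used but have different finding in the same time window". Appendix 12.1 is then applied and "Finding from higher visibility image will be used for analysis". Neither sentence mentions when the images were taken.
- **Same image type.** The text for repeat readings is "from the same type of image in the same time window, then the assessment closest to the target day will be used"; it is limited to the event rate at a given time point. This is the only place where SAP 8.1 uses the date to choose between images.

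In Appendix 12.1 the row "Stent graft fracture" scores abdominal X-ray 1 (best), contrast CT 2 and non-contrast CT 3.

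Protocol H.1 differs. It takes the assessment closest to the target day, whatever the image type, and has no rank.

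SAP 8.5 sends device deficiencies to Table 3 in SAP 8.4, which has two blocks. The *At* block counts subjects with an event in a single window, over subjects with a readable image in that window. The *Through* block is cumulative. Its 12-month numerator is "No. of subjects who had an event with scan day within 1-, 6- or 12-month windows", and its denominator begins "No. of subjects who had an event (counted in m) or had a readable image". The device-deficiency endpoint named in SAP 5 is a *Through* rate at 6 and 12 months. SAP 5 also has secondary endpoints assessed annually to 5 years.

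**The concern.** Ranking by visibility makes sense when two images show the device at about the same moment and one is the better witness. It does not suit images taken weeks or months apart. A stent fracture does not heal, so a clear X-ray followed by a CT showing a fracture need not be a conflict: the stent may have broken in between. The rule treats the pair as a conflict and lets the older image win.

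Such pairs are foreseeable. Protocol F.2.3 requires both CT/MR and X-ray at each follow-up visit, but they need not be on the same day. The Data Monitoring Committee has recommended imaging beyond the schedule, and Protocol F.3 says: "Any interim imaging of the stent graft region but not linked to a study visit should be sent to the Core Lab".

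The failures concerned matter most in this trial. Protocol C.5 names transition stent fracture and suprarenal stent fracture among the reasons enrolment ended, and J.3 says the observed failures occur at higher rates than with other commercial devices. For a permanent failure, letting an earlier clear image override a later true positive can only lower the reported rate.

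If the subject stays in the trial, a lasting fracture can be picked up in the next window. If the subject leaves, it cannot. Protocol F.2.3 states: "If conversion to open repair is required during the follow-up period, then the subject will be followed for 30 days after the conversion", after which the subject exits.

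**Working it through.** The plan gives no figure for the effect of this rule, so there is none to reproduce. The check applies the written rules to dated images.

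**1. Window widths** (SAP Table 1; last day − first day + 1)

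| Window | Days | Width |
|---|---|---|
| 6 months | 91–304 | 214 |
| 12 months | 305–548 | 244 |
| 2 years | 549–913 | 365 |
| 3 years | 914–1278 | 365 |
| 4 years | 1279–1644 | 366 |
| 5 years | 1645–2009 | 365 |

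The windows behind the named endpoint are 214 and 244 days wide. Only the annual ones reach 365 or 366.

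**2. A case that isolates the rank rule** (12-month window, target day 365)

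X-ray clear on day 335. The only CT, on day 380, shows a fracture. Conversion on day 400; exit on day 400 + 30 = 430. Both images lie inside the visit window of Protocol Table F-1 (days 335–421), so no unscheduled imaging is needed.

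| Rule | X-ray, day 335 | CT, day 380 | Finding used |
|---|---|---|---|
| SAP 8.1 (rank) | 1 | 2 | X-ray: no fracture |
| Protocol H.1 (distance from day 365) | 30 days | 15 days | CT: fracture |

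There is one image of each type, so the same-type rule is not triggered and the rank alone decides. The subject has a readable image and enters the 12-month *At* rate as a non-event. The next window opens on day 549, after the exit on day 430, so no later window corrects it.

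**3. The closest-day rule**

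X-ray and CT clear on day 365; an interim CT on day 456 shows a fracture. The two CTs are the same type, at distances 0 and 456 − 365 = 91 days, so SAP 8.1 takes day 365. Protocol H.1 does the same. The closest-day rule alone explains this loss, without the rank.

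The exposure is structural. After a visit closes there are 304 − 213 = 91 further days in the 6-month window and 548 − 421 = 127 in the 12-month window. An image on any of those days is farther from target than every on-time image: at least 214 − 183 = 31 days against at most 30, and at least 422 − 365 = 57 against at most 56. These are calendar days, not a measure of bias.

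**4. The *Through* rate for the case in step 2**

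- Table 3 applied directly: the day-380 scan is an event with a scan day in the 12-month window, so the subject counts.
- SAP 8.1 applied first: the 12-month finding is already no fracture, so the subject is a non-event with a readable image.

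No sentence in SAP 8.1, 8.4 or 8.5 says which comes first.

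**5. Size per affected subject**

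1/69 = 1.4 percentage points if all 69 enrolled subjects have readable images; 1/40 = 2.5 points for the regulatory cohort. Readable-image counts are not given, so these denominators are assumptions. The number of affected subjects depends on the Data Monitoring Committee's imaging interval and on how many subjects leave early. Neither is in the documents.

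**The case against.** The strongest objection is that the named endpoint escapes. SAP 8.1 introduces its windows for by-visit summaries, and its closest-day sentence is limited to rates at a given time point. The *Through* block of Table 3 has its own numerator and a denominator built to keep earlier events in. Read naturally, it counts any positive scan. This largely stands. A reader might infer that the fracture in step 2 is never counted anywhere in the device-deficiency analysis; the documents do not establish that. They establish it for the *At* rate only. But the rank sentence, unlike the closest-day sentence, is not limited to rates at a time point, and nothing exempts the *Through* rates from it. Two statisticians could report different *Through* rates from the same data.

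A second objection is that the events are recorded elsewhere. Conversion has its own endpoint. Device deficiencies with SAE potential are reported within 3 calendar days (Protocol Table F-4), explanted devices are to be returned (E.6.3), and the Data Monitoring Committee reviews safety data. This stands too. A reader might infer that the worst failures disappear from the trial; they do not. What can be too low is the imaging-based rate, which is the planned summary of these failures.

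A third objection is that the trial is descriptive, enrolment has ended, and J.3 already acknowledges the higher failure rates. That limits the consequence. It does not make the selection rule right.

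**Conclusion.** The defect holds as a stated rule. With no date condition and X-ray ranked above CT for fracture, an earlier clear X-ray overrides a fracture first seen on a later CT in the same window. By-visit rates are then too low, permanently so when the subject leaves before the next window. The closest-day rule has the same effect on fractures first seen on interim images after an on-time clear scan, and there SAP 8.1 and Protocol H.1 agree. In the rank case they can give opposite answers.

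The named 6- and 12-month *Through* endpoint is affected only if the 8.1 selection is made before Table 3 is applied. That is an ambiguity to settle, not a demonstrated undercount.

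The size is 1.4 points per affected subject at n = 69 and 2.5 at n = 40, assuming all have readable images. A reader may want a percentage of fractures missed, but any such figure would only restate an assumed interim-imaging gap and an assumed leaving fraction. The conclusion also assumes that the later CT reading is true and that the Table 3 method carries on to the annual visits, for which the SAP gives no separate formula. Primary endpoints, the conversion endpoint and individual device-deficiency reports are unaffected.

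**What to change.** In SAP 8.1:

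- Apply the Appendix 12.1 rank only to images from the same visit. Define this by closeness in time, not by the Table F-1 window, because days 335 and 380 in the example share that window. A limit such as 14 days would do; the exact number is a matter of choice.
- For stent fracture, anchoring pin fracture and detachment, count the subject as an event from the first image on which the core lab reports it, and do not apply the closest-day rule. State that the rank still settles a same-visit disagreement before this step.
- State that *Through* rates count any core-lab positive scan to date, unless the core lab withdraws the reading.

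The cost is wording. No new images or visits are needed, since Table 3 already works from scan day and readable images. The departure from Protocol H.1 can be described and justified in the final report, as section H allows. The downside is that a false-positive CT reading is carried forward until the core lab withdraws it.

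Optional clarifications: add a detachment row to Appendix 12.1, which has none; report rates by the deficiency types in Protocol L.2; and label wireform fractures by stent location, if the core lab records it.
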